- 2) Days 3-6: All subjects will be seen on the CRSU on days 3 and 6, and at the IDAS clinic on days 4 and 5. On days 3-6, subject group A will receive one placebo pill twice daily, and group B will receive one placebo pill in the morning and one matching lorcaserin 10 mg pill in the evening, for a total dose of 10 mg daily. ECG with QTc will be performed daily. If the QTc is prolonged greater than 30ms over baseline lorcaserin dosage will be held.
- 3) Day 7: All subjects will receive one placebo pill in the morning in single blind fashion. Following Cocaine Self-administration sessions and impulsivity testing the subjects will leave the unit.
- 4) Days 8-10: All subjects will be seen at the IDAS clinic on Days 8 and 9 and subjects in group B will have a blinded dosage increase to 10 mg of lorcaserin twice daily for Days 8-11 (Days 10 and 11 will take place at the CRSU). Vital signs including heart rate, blood pressure and respiration rate will be obtained before placebo/lorcaserin administration. ECG with QTc will be performed daily under the supervision of a study physician. If the QTc is prolonged greater than 30ms over baseline lorcaserin dosage will be held.
- 5) Day 11: All subjects will be seen on the CRSU and receive placebo/lorcaserin in the morning followed by the last cocaine self-administration session.
- 6) Day 12: Subjects will be seen at IDAS for study procedures.
- 5) Cocaine Infusion Sessions (Days 1, 2, 6, and 10): All subjects will undergo an ascending dose intravenous cocaine administration after admission on day 1 to ensure safety of later cocaine studies.

To assess the safety and subjective effects of cocaine in the presence of lorcaserin, subjects will receive ascending doses of intravenous cocaine (10 mg, 20 mg, 40 mg), with each cocaine administration separated by

one hour. In addition, 0 mg cocaine (saline) infusion will be randomly given after the first dose of cocaine in order to aid in blinding investigators and subjects to the order of drug administration. Infusions will be carried out hourly starting from 1 hour after placebo/lorcaserin for 4 times (on Day 1, 2, 6, and 10). An example dose by session diagram is shown below. Note that the 0 mg dose is randomly given after the first dose of cocaine. Monitoring will be continued for 1 hour after the last dose of cocaine.

Dose	Dose Session 1	Dose Session 2	Dose Session 3	Dose Session 4
1	10 mg Cocaine	10 mg Cocaine	10 mg Cocaine	10 mg Cocaine

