Procedure Afternoon Session	Cocaine Self Administration Depart from CRS			Three Doses of Cocaine (NexFin monitoring) Cardiovascular & Subjective Ratings Cardiac Biomarkers (4-6 hrs from last dose) Depart from CRS	Cocaine Self Administration Impulsivity Testing Depart from CRS
Study Drug	Placebo 8:00 a.m., Lorcaserin 10mg p.m. prior to departure or Placebo 8:00 a.m., Placebo p.m. prior to	Placebo 8:00 a.m., Lorcaserin 10mg p.m. prior to departure or Placebo 8:00	Placebo 8:00 a.m., Lorcaserin 10mg p.m. prior to departure or Placebo	Placebo 8:00 a.m., Lorcaserin 10mg p.m. prior to departure, or Placebo 8:00 a.m., placebo p.m. prior to departure	Placebo 8:00 a.m.

	departure	a.m., placebo p.m. prior to departure	8:00 a.m., placebo p.m. prior to departure		
--	-----------	--	---	--	--

Study Day	Day 8	Day 9	Day 10	Day 11	Day 12
Study Visit	Eight	Nine	Ten	Eleven	Twelve
Procedure Morning Session	Arrive at IDAS ECG	Arrive at IDAS ECG	Arrive at CRS ECG 10mg Cocaine for PK, Lorcaserin blood levels	Arrive at CRS ECG Cocaine Self Administration	Arrive at IDAS ECG Impulsivity Testing
Procedure Afternoon Session			Three Doses of Cocaine (NexFin monitoring) Cardiovascular & Subjective Ratings Cardiac Biomarkers (4-6 hrs from last dose) Impulsivity Testing Depart from CRS	Cocaine Self Administration Depart from CRS	Physical exam
Study Drug	Lorcaserin 10mg 8:00 a.m., Lorcaserin 10mg p.m. prior to departure. or Placebo 8:00 a.m., placebo p.m. prior to departure	Lorcaserin 10mg 8:00 a.m., Lorcaserin 10mg p.m. prior to departure or Placebo 8:00 a.m., placebo p.m. prior to departure	Lorcaserin 10mg 8:00 a.m., Lorcaserin 10mg p.m. prior to departure or Placebo 8:00 a.m., placebo p.m. prior to departure	Lorcaserin 10mg 8:00 a.m. or Placebo 8:00 a.m.,	

Self-Administration Session (Days 3, 7, and 11)

On days 3, 7, and 11, subjects participate in two self-administrative sessions and will make six choices for cocaine or \$5. The first session will begin at 10 am and the second at 1 pm (see Table 3 below), with each session being 2.5 hours long.

Table 3. Schedule of Cocaine Self Administration Procedure

Time	Choices	8 patients	8 patients
10:00 am	Baseline: VAS, BP/HR, EKG		
10:20 am	Choice 1	0 mg cocaine IV or \$ 5	25 mg cocaine IV or \$ 5
10:35 am	Choice 2	0 mg cocaine IV or \$ 5	25 mg cocaine IV or \$ 5

10:50 am	Choice 3	0 mg cocaine IV or \$ 5	25 mg cocaine IV or \$ 5
11:05 am	Choice 4	0 mg cocaine IV or \$ 5	25 mg cocaine IV or \$ 5

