11:20 am	Choice 5	0 mg cocaine IV or \$ 5	25 mg cocaine IV or \$ 5
11:35 am	Choice 6	0 mg cocaine IV or \$ 5	25 mg cocaine IV or \$ 5
1:00 pm	Baseline: VAS, BP/HR, EKG		
1:20 pm	Choice 1	25 mg cocaine IV or \$ 5	0 mg cocaine IV or \$ 5
1:35 pm	Choice 2	25 mg cocaine IV or \$ 5	0 mg cocaine IV or \$ 5
1:50 pm	Choice 3	25 mg cocaine IV or \$ 5	0 mg cocaine IV or \$ 5
2:05 pm	Choice 4	25 mg cocaine IV or \$ 5	0 mg cocaine IV or \$ 5
2:20 pm	Choice 5	25 mg cocaine IV or \$ 5	0 mg cocaine IV or \$ 5
2:35 pm	Choice 6	25 mg cocaine IV or \$ 5	0 mg cocaine IV or \$ 5

In one session subjects will make six choices between 0 mg i.v. cocaine or money. During the other self-administration session, subjects will make six choices between 25 mg i.v. cocaine or money. The dose of cocaine was chosen based on previous studies showing a significant medication effect on cocaine self-administration (Hart *et al*, 2008). Sessions begin with a baseline period in which participants complete computerized subjective-effects questionnaires, and vital signs are monitored.

The session begins with one “sample” choice, where participant respond on a keyboard under a fixed ratio schedule (FR200; participants are required to press the spacebar 200 times to receive the option). The subsequent five trials are spaced 15-min apart, in which participants had the opportunity to self-administer the same dose of cocaine as the sample dose, or to receive money. A modified progressive ratio of responding is used, in which the first response requirement is a FR200. Following each choice, the response requirement for the chosen option increases by 400, while the response requirement for the non-chosen option does not change. Thus, if a participant only chose cocaine or only chose money, the response requirements would escalate progressively through 600, 1,000, 1,400, 1,800, and 2,200 bar presses (Haney *et al*, 2011).

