The subject would make a series of choices using the PR schedule between ascending value money options (\$5) or cocaine (0 mg or 25 mg/i.v. infusion) using a patient controlled (PCA pump). Choices for money will be verbally indicated to the investigator. Infusions will be made over a 2 min period followed by a 13 min time-out period. Subjects will receive the cash or cocaine doses (0 or 25 mg) immediately after they meet the progressive ratio criteria for each choice, providing vital signs remain within the preset intervals. If the subject chooses all cocaine options in the cocaine choice session and no money, they will receive a maximum of 120 mg cocaine, i.v. Money choices will be given directly to the patient after choice session, but this can only be spent after departing from the CRS. All infusions on this day will be double-blinded and counterbalanced in their presentation among subjects.

Cardiovascular Monitoring During Cocaine Infusions and Cocaine Self-Administration Procedure

Cardiovascular monitoring by continuous measuring heart rate/ECG and blood pressure starting 15 minutes prior to each of the 4 cocaine infusions and continued for at least 60 minutes following each dose. PI/Co-I or their medically qualified designees will be present during all cocaine infusions to monitor and intervene if necessary. For the sessions of cocaine infusions on Day 1, 2, 6, and 10, non-invasive monitoring of cardiac hemodynamics will be performed with the NexFin finger cuff system (Edwards Life Sciences).

Criteria for withholding Cocaine Administration

Cocaine administration will not be initiated if:

- Clinically significant arrhythmias
- Resting pulse > 130 bpm
- QTc increase of greater than 30ms over baseline
- Blood pressure above 165mm Hg systolic and 100mm Hg diastolic.
- Behavioral manifestations of cocaine toxicity (agitation, psychosis, inability to cooperate with study procedures).

If cardiovascular measures have not returned to acceptable levels (heart rate <130 bpm, diastolic pressure <100mmHg, and systolic pressure <165 mmHg, QTc <30ms over baseline), the next session will be delayed by 15 min, after which these measures will be repeated.

Stopping Criteria for Subject Participation

Subject participation will be terminated if any of the following events occur:

The following values do not return to acceptable limits within appropriate time frames (approximately 30 minutes);

- Systolic BP > 180 mm Hg
- Diastolic BP > 120 mm Hg

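### The stated 120 mg maximum of self-administered IV cocaine per active session contradicts the protocol's own schedule, which allows 150 mg

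*Combined protocol and SAP*

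**What the plan says.** On Days 3, 7 and 11, "subjects participate in two self-administrative sessions and will make six choices for cocaine or" a $5 payment in each session. One session offers 0 mg cocaine; in the other, "subjects will make six choices between 25 mg i.v. cocaine or money". Table 3 lists Choices 1 to 6 for each session, with 25 mg offered at all six in the active one.

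The text below Table 3 describes a sample choice at a fixed ratio of 200 presses and then says: "The subsequent five trials are spaced 15-min apart". These later trials use the same dose as the sample. For a subject who always picks the same option, the requirement after the first 200 presses will "escalate progressively through 600, 1,000, 1,400, 1,800, and 2,200 bar presses".

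The delivery rule is that the chosen cash or dose (0 or 25 mg) is given "immediately after they meet the progressive ratio criteria for each choice, providing vital signs remain within the preset intervals". The same paragraph then states, of subjects who take every cocaine option, that "they will receive a maximum of 120 mg cocaine, i.v".

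**The concern.** The 120 mg figure is presented as the result of choosing cocaine every time, yet it does not match the number of choices multiplied by the dose. It is also the only cumulative ceiling the protocol gives for self-administered cocaine.

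The section on the risks of lorcaserin combined with cocaine says the combination has not been studied in humans, and relies on ascending cocaine doses with criteria to stop escalation. The self-administration session does not ascend: it repeats 25 mg at a nominal 15-minute spacing. On Days 7 and 11 it follows lorcaserin dosing in Group B. It is also the largest scheduled cocaine exposure on any study day, so a reader who relies on the stated maximum understates the exposure at its highest point.

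There is a practical problem as well. Staff who follow Table 3 may exceed the written maximum. Staff who hold to 120 mg would have to cut the fifth infusion to 20 mg and withhold the sixth, for which the protocol gives no instruction. That would fall on the heaviest cocaine choosers, and cocaine choice is a primary outcome.

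**Working it through.** **Inputs**, all from the self-administration section unless noted:
- Dose per cocaine choice in the active session: 25 mg (text and Table 3).
- Choices per session: 6 (text and Table 3, Choices 1 to 6).
- Cross-check from the trial structure: 1 sample + 5 later trials = 6.
- Cross-check from the ratio steps: 200, 600, 1,000, 1,400, 1,800, 2,200, which is six steps.
- Other session on the same day: 0 mg, so it adds nothing.
- Stated maximum: 120 mg.

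**Attempt to reproduce the stated figure.** Maximum = number of infusions × 25 mg.

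| Reading | Infusions | Total |
|---|---|---|
| Four infusions | 4 | 100 mg |
| Sample not counted | 5 | 125 mg |
| Schedule as written | 6 | 150 mg |
| Sample counted as an extra | 7 | 175 mg |

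None gives 120 mg. In reverse, 120 / 25 = 4.8 infusions, which is not a whole number. To reach 120 mg would take 6 × 20 mg or 5 × 24 mg, and neither dose is used in these sessions. A carry-over from a 20 mg unit dose is possible, but the documents do not say so.

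**Size of the discrepancy.** 150 − 120 = 30 mg, and 150 / 120 = 1.25, so the scheduled maximum is 25% above the stated one. Over the three self-administration days the totals are 3 × 150 = 450 mg against 3 × 120 = 360 mg. Over Days 7 and 11 they are 300 mg against 240 mg. These totals repeat the same 25%.

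**Comparison with the fixed-dose sessions** (Dosage/Dosage Regimen, cocaine infusion sessions). One session gives 10 + 20 + 40 = 70 mg at hourly spacing.
- Against 70 mg: 150 / 70 = 2.14, where the stated figure implies 120 / 70 = 1.71.
- Table 2 lists a separate 10 mg PK dose on Days 2, 6 and 10, so the total on those days is 80 mg. Against 80 mg: 150 / 80 = 1.88, where the stated figure implies 120 / 80 = 1.50.

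**Timing.** By Table 3, Choice 1 is at 10:20 and Choice 6 at 11:35. That is 75 minutes, plus a 2-minute infusion, or 77 minutes. This is the nominal minimum and allows no time for pressing.

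**The case against.** The strongest reply is that the schedule offers 150 mg but need not deliver it. A subject must complete 200 + 600 + 1,000 + 1,400 + 1,800 + 2,200 = 7,200 presses, with vital signs within limits before each infusion. The 120 mg could also be an intended limit whose operating rule was left out. The first part is true of what a given subject receives, but the sentence states the maximum for someone who takes every option, and that is 150 mg. As a cap, 120 mg does not work with fixed 25 mg infusions: four give 100 mg and the fifth reaches 125 mg.

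The monitoring paragraph that follows refers to four cocaine infusions. That fits the fixed-dose sessions, which have four infusions including saline, and not self-administration.

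Some points do stand:
- The 77 minutes is a lower bound. The 2-minute infusion and 13-minute time-out already fill each 15-minute interval. If pressing follows the time-out, the 7,000 presses after Choice 1 add about 19 to 39 minutes at an assumed 6 to 3 presses per second.
- For days with the PK dose, the fair comparison is 150 mg against 80 mg.
- No sample size, analysis, withholding rule or stopping rule uses the 120 mg figure.
- The analysis section already names choice selection as the outcome, which largely settles that choices are what is counted.

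**Conclusion.** The concern holds. The scheduled maximum is 150 mg per active session, 30 mg (25%) more than stated, and no reading of the schedule gives 120 mg. The conclusion assumes only that the six choices and the 25 mg unit dose are as written; text, table and ratio steps agree on the number of choices, and text and table agree on the dose.

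The error should be fixed. It misstates the highest cocaine exposure in the trial and leaves staff with two instructions that cannot both be followed. Its consequence is limited because the unit dose, the spacing and the vital-sign rules govern what is actually given. Whether the consent form, pump settings or monitoring-board material carry 120 mg cannot be seen from the documents.

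**What to change.** The sponsor should first confirm which figure was intended.

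- **If the schedule stands:** restate the maximum as 150 mg per active session (6 × 25 mg), and check that the consent form, pump settings and DSMB material agree.
- **If a lower limit was meant:** set an explicit cap of 100 or 125 mg, say what happens at the remaining choices once it is reached, and state that the endpoint counts choices made and not infusions delivered.

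The first option is a short wording change plus a check of linked documents. It still needs prior written IRB approval under Protocol Amendments, and it raises the stated maximum exposure, so reviewers must be content with 150 mg in this combination. The second option keeps exposure lower, but removes one or two infusions from subjects who choose cocaine throughout.

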This is a single center, double-blind, placebo-controlled, randomized, 1b/2a study. 18 subjects are planned. Screening data will be reviewed to determine subject eligibility. Subjects who meet all inclusion criteria and none of the exclusion criteria will be entered into the study.

The following treatment regimens will be used:

Lorcaserin will be 10mg once daily increasing to 10mg twice daily.

Placebo or Comparator – identical placebo capsules administered at the same time as lorcaserin.

Subject participation will consist of 12 active study days and 2 follow-up visits, divided into multiple scheduled study visits. Total duration of the study is expected to be 4 years.

Criteria for evaluation

Primary Efficacy Endpoint

1. Safety: Heart rate (HR) and blood pressure (BP) measures during saline infusions will be compared to HR and BP after each cocaine infusion (20 mg and 40 mg doses). Changes in HR and BP induced by cocaine infusion along with lorcaserin will be compared to those without lorcaserin, by cocaine dose level (20 mg and 40 mg doses), using repeated measures analysis of variance (ANOVA). Changes in ECG readings during saline infusion as compared to those taken during cocaine infusions will be reported as summary statistics. Adverse event data will be compiled for lorcaserin and placebo cohorts and presented as summary statistics.
2. Cocaine Self-administration: Repeated measures ANOVA with cocaine dose (0mg, 25mg) and lorcaserin dose (0mg, 10mg, 20mg) as within subject factors will be used to examine differences in mean cocaine choice selection. In addition, a Bayesian analysis will be carried out as described below.
3. Subjective response to cocaine: Subjective response measures (VAS) obtained during saline infusions will be compared between lorcaserin and placebo subjects to those during cocaine infusions by cocaine dose level to determine the extent to which these measures are modified by the administration of lorcaserin using repeated measures ANOVA.
4. Cocaine PK: Plasma concentration-time profiles of cocaine after cocaine infusion during placebo administration (Day 2) will be analyzed to obtain pharmacokinetic parameter estimates of cocaine (T_{max}, AUC, apparent t_{1/2}, CL) by individual. These parameters will be compared within subjects on sessions with lorcaserin (Days 6 and 10).

Secondary Efficacy Endpoints

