Each pill bottle of study drug will be labeled with the required FDA warning statement, the protocol number, a treatment number, the name of the study physician, and directions for patient use and storage.

Administration of Study Drug

Dosage/Dosage Regimen

If subjects meet inclusion criteria, they will be seen both in the hospital and at IDAS clinic for a total of 12 active study days and monitoring procedures will be in place to detect drug and alcohol use and assess for adverse events at each visit. In addition, the hospital cocaine administration procedures will reduce the likelihood of increased cocaine craving after cocaine administration. Subjects will undergo procedures as described below. Subjects will not be allowed to smoke cigarettes, as smoking is not allowed in the hospital or anywhere on the VCU campus. Subjects will have the option to use a nicotine patch dosed based on the amount of daily cigarettes smoked. Subjects will not be allowed to leave the CRS Unit nor receive visitors during their study visits. Subjects who are unable to comply with these restrictions will be dropped from the study. After a screening cocaine infusion to determine safety, eligible subjects will be randomized to Group A –placebo only or Group B –placebo followed by an ascending dose of lorcaserin. Six subjects will be assigned to Group A (placebo) and 12 subjects will be assigned to Group B (active lorcaserin).

Study Drug Dosage: Lorcaserin will be 10mg once daily increasing to 10mg twice daily.

Outcome Measures: The primary outcome measures are adverse events, cardiovascular responses (Heart rate (HR), blood pressure (BP), ECG measurements, subjective response to cocaine, cocaine self-administration, and cocaine blood PK. Secondary outcome measures will be impulsivity as measured by the immediate memory task (IMT).

- 1) Days 1-2: All subjects will be seen on the CRSU. All subjects will receive placebo on days 1-2 in a single blind fashion. Vital signs including heart rate, blood pressure and respiration rate will be obtained after placebo administration. Days 1-2 will be single-blind placebo, whereas all remaining study days will be double-blind. All subjects will leave the CRSU at the end of each study day.

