Children as defined by NIH (age 18-21 years) will be included in this research. The incidence of severe cocaine abuse/dependence is relatively small in the population of youth less than 18 years old. From a safety perspective, risks of exposure to the proposed study medication and cocaine administration in substance-dependent children under 18 have not been established.

Analysis of Primary Endpoint

1. Safety: Heart rate (HR) and blood pressure (BP) measures during saline infusions will be compared to HR and BP after each cocaine infusion (20 mg and 40 mg doses). Changes in HR and BP induced by cocaine infusion along with lorcaserin will be compared to those without lorcaserin, by cocaine dose level (20 mg and 40 mg doses), using repeated measures analysis of variance (ANOVA). Changes in ECG readings during saline infusion as compared to those taken during cocaine infusions will be reported as summary statistics. Adverse event data will be compiled for lorcaserin and placebo cohorts and presented as summary statistics.
2. Cocaine Self-administration: Repeated measures ANOVA with cocaine dose (0mg, 25mg) and lorcaserin dose (0mg, 10mg, 20mg) as within subject factors will be used to examine differences in mean cocaine choice selection. In addition, a Bayesian analysis will be carried out as described below.
3. Subjective response to cocaine: Subjective response measures (VAS) obtained during saline infusions will be compared between lorcaserin and placebo subjects to those during cocaine infusions by cocaine dose level to determine the extent to which these measures are modified by the administration of lorcaserin using repeated measures ANOVA.
4. Cocaine PK: Plasma concentration-time profiles of cocaine after cocaine infusion during placebo administration (Day 2) will be analyzed to obtain pharmacokinetic parameter estimates of cocaine (Tmax, AUC, apparent t_{1/2}, CL) by individual. These parameters will be compared within subjects on sessions with lorcaserin (Day 6 and 10).

Analysis of Secondary Endpoints

Response inhibition: Commission errors on the IMT will be compared between lorcaserin and placebo subjects to determine the extent to which this measure is modified by the administration of lorcaserin using repeated measures ANOVA.

Safety and tolerability data will be summarized by treatment group.

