Adverse event rates will be coded by body system and MedDra classification term. Adverse events will be tabulated by treatment group and will include the number of patients for whom the event occurred, the rate of occurrence, and the severity and relationship to study drug.

Interim Analysis

When approximately 50% of patients have completed the study, an interim analysis for safety will be conducted by the DSMB. Serious adverse events will be monitored by the committee on an ongoing basis throughout the study.

Sample Size and Randomization

This project requires a final sample size of 18 subjects (Six subjects assigned to Group A (placebo) and 12 subjects assigned to Group B (active lorcaserin)). This sample size for effect of lorcaserin on cocaine self-administration was based on previous research showing effects of medication on human cocaine self-administration (Hart et al, 2008). In an effort to increase the power of the study, a Bayesian approach will also be utilized that incorporates information from previous studies. This approach will use a Bayesian hierarchical model with subject at the lowest level of the hierarchy and treatment group at the second level. This model is analogous to the repeated measures ANOVA except that prior information will be introduced. Since many similar studies have been conducted with cocaine users and the same outcome measures we will assign an

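### Order of the 0 mg and 25 mg choice sessions is tabulated for 16 of 18 subjects; balance within arm and a fixed order per subject are not specified, and the ANOVA has no period term

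*Combined protocol and SAP*

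**What the plan says.** - **Planned size.** The section Sample Size and Randomization gives the total and the split: "This project requires a final sample size of 18 subjects (Six subjects assigned to Group A (placebo) and 12 subjects assigned to Group B". The Study Overview and Dosage/Dosage Regimen sections agree ("18 subjects are planned"; "Six subjects will be assigned to Group A (placebo) and 12 subjects will be assigned to Group B (active lorcaserin"). Withdrawn subjects are replaced (Replacement of Subjects).
- **Session order.** Table 3 has two order columns, headed "8 patients 8 patients": 0 mg then 25 mg, and 25 mg then 0 mg. The only rule on assignment is in the Self-Administration Session text: "All infusions on this day will be double-blinded and counterbalanced in their presentation among subjects". Arm is not mentioned there. The randomisation passages name arm and gender only.
- **Timing.** "The first session will begin at 10 am and the second at 1 pm". In Table 3 the last morning choice is at 11:35 am, a new baseline follows at 1:00 pm, and afternoon choices run from 1:20 to 2:35 pm.
- **Analysis.** Analysis of Primary Endpoint, item 2: "Repeated measures ANOVA with cocaine dose (0mg, 25mg) and lorcaserin dose (0mg, 10mg, 20mg) as within subject factors". No order or period term is listed. A detailed SAP is still to be written before the final analysis.

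**The concern.** Cocaine choice is a primary outcome and the basis of the sample size. Its two sessions fall on one day and are not exchangeable: the afternoon session follows a full morning of choices, work and possibly cocaine. Which session falls in the afternoon therefore matters, and the plan should say how that is decided.

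The tabulated counts do not add up to the planned number. Beyond the general counterbalancing statement, nothing says whether order is balanced within each arm, whether a subject keeps one order on all three days, or which order a replacement receives. The Day 3-7 and Day 8-12 visits may be scheduled separately within a 90-day limit, so order could slip between them. With six placebo subjects, one or two subjects in the other order change the arm's balance noticeably.

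**Working it through.** **1. Count.** Planned: 6 + 12 = 18, which reproduces the stated total. Table 3: 8 + 8 = 16. The gap is 2, and a patient count per order has to be exact. Because withdrawals are replaced, dropout does not explain it.

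**2. Chance imbalance.** Assume order is 9/9 over all 18 subjects without regard to arm. The number of the six placebo subjects in a given order is then hypergeometric, with C(18,6) = 18,564 equally likely sets.
- 3/3: C(9,3)² / 18,564 = 84² / 18,564 = 7,056 / 18,564 = 0.380
- 5:1 or 6:0, either way: 2 × (126 × 9 + 84) / 18,564 = 2,436 / 18,564 = 0.131

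A 4:2 placebo split leaves the lorcaserin arm at 5:7, so the arms differ by 4/6 − 5/12 = 25 percentage points in the share with a given order. A 5:1 split gives 5/6 − 4/12 = 50 points.

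**3. What can reach which choices.** The 25 mg session is either in the morning, with no earlier session that day, or in the afternoon after the 0 mg session. Cocaine from the same day's choice sessions can therefore reach only afternoon 0 mg choices. Afternoon 25 mg choices are exposed to time of day and to fatigue: a subject who always picks the same option makes 200 + 600 + 1,000 + 1,400 + 1,800 + 2,200 = 7,200 bar presses in the morning.

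**4. Possible size of carry-over.** From 11:35 am to 1:20 pm is 105 minutes. The documents give no half-life, so it is assumed. With first-order decay, the residue at 1:20 pm is 25 mg × Σ 2^(−(105 + 15k)/t½), with k = 0 to 5 for six infusions and k = 0 to 4 for the last five.

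| Assumed t½ (min) | 20 | 40 | 60 | 90 |
|---|---|---|---|---|
| Six infusions (mg) | 1.5 | 14 | 30 | 51 |
| Last five only (mg) | 1.5 | 13 | 27 | 45 |

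The stated session maximum of 120 mg matches neither 5 × 25 = 125 mg nor 6 × 25 = 150 mg. These passages must be reconciled before the residue can be settled. The protocol's own PK sampling runs to 240 minutes after a 10 mg dose, so afternoon choices, 105 to 180 minutes after the last morning choice, lie inside that window.

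**5. Where order enters the estimates.** Let π be the effect of being in the afternoon, λ the carry-over into an afternoon 0 mg session, and p the share of an arm with the 25 mg session in the afternoon.
- 25 mg minus 0 mg in one arm on one day: true contrast + p(2π + λ) − (π + λ). At p = 1/2 this is the true contrast − λ/2.
- Difference between arms in that contrast: (2π + λ) times the difference in p, so 0.50 × (2π + λ) under a 5:1 placebo split.
- Change from Day 3 in 25 mg choices: pπ − pπ = 0 if each subject keeps one order and π is constant. If an arm's share moves from p to p′, the change is shifted by (p′ − p)π.
- If π drifts over days alike in both arms, the arms differ by the difference in p times the drift, which is zero under balance within arm. If the drift differs by arm, balance does not remove it.

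**The case against.** The strongest reply is that the planned comparison is within subject and the power calculation uses paired differences. If each subject keeps one order, an additive order effect cancels from the change since Day 3 even under a 5:1 or 6:0 placebo split. This stands, and it limits what the 0.38 and 0.13 mean. One Table 3 serves all three days and its columns are groups of patients, so one order per patient is the natural reading, though it is not stated.

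A reader might infer three stronger things that the documents do not support:
- **That order is unbalanced within arm.** The text neither promises nor excludes balance, and the randomisation list is not in the documents.
- **That two subjects have no order.** The counterbalancing rule covers all subjects; only the tabulated counts fall short.
- **That leftover cocaine distorts the 25 mg choices, and so the lorcaserin effect on cocaine choice in general.** Table 3 rules out the first part, and step 5 limits the second.

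The plan also has a fresh 1:00 pm baseline and a 15-minute delay if cardiovascular values have not recovered. These are relevant, but they do not amount to a washout rule. The promised SAP could set model terms, but it cannot repair how order was assigned.

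**Conclusion.** The point holds in a limited form. The count mismatch, 16 against 18, is certain. Balance within arm, a fixed order per subject and the order of replacements are unspecified, and the ANOVA omits period.

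The exposed quantities are the 0 mg versus 25 mg contrast and its interaction with lorcaserin. The lorcaserin effect on change from Day 3 is biased only if order changes between days, or if the order effect interacts with treatment or day. Such an interaction is plausible for the 0 mg choices, because carry-over depends on how much cocaine was chosen in the morning, which lorcaserin is meant to change. Its size cannot be fixed from the documents: the residue runs from about 1.5 to 51 mg over assumed half-lives of 20 to 90 minutes. The 0.38 and 0.13 assume 9/9 order assigned without regard to arm.

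This does not invalidate the trial. It is an avoidable source of bias and noise in a primary outcome with six controls.

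**What to change.** 1. Correct Table 3 to 9 + 9.
2. Counterbalance order within arm in the pharmacy list: 3/3 placebo and 6/6 lorcaserin.
3. State that each subject keeps the same order on Days 3, 7 and 11, and that a replacement takes the order of the subject replaced.
4. Add session period (morning or afternoon, equivalent to order-by-cocaine-dose) to the choice model, with order-by-lorcaserin-dose as a sensitivity term. A main effect of order alone is between subjects and would leave the within-subject contrasts unadjusted.
5. Reconcile the stated session maximum with the number of choices and the dose per choice.

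**Cost.** A revised list and a few degrees of freedom: one for period, and (2 − 1) × (3 − 1) = 2 for the sensitivity interaction. A subject could anticipate a fixed order by Day 7.

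**Limits.** The period term handles time of day. It does not remove the λ/2 that carry-over leaves in the 0 mg versus 25 mg contrast. A morning-only analysis avoids carry-over but compares cocaine doses between about 3 and 3 placebo subjects, so it is descriptive at most.
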